- k Both non-serious adverse events and serious adverse events will be collected through 30 (+5) days after the last dose of protocol-required therapies (romiplostim/placebo [IP], chemotherapy [non-IP] up to 3 cycles). Note: For subjects who discontinue IP prior to completing 3 cycles of chemotherapy, non-serious adverse events should be collected through 3 on study chemotherapy cycles. Serious adverse events will be collected through the EOS. For the whole duration of the LTFU period, non-serious adverse events will be collected through EOS only if mandated by country-specific requirements.
- l Subjects will be followed for the diagnosis of, or progression to, secondary malignancies (including myeloid malignancies) or myelodysplastic syndromes, as well as vital status and cause(s) of death. During the treatment period, disease status assessment will be performed on day 1, week 8 ( $\pm$  2 weeks), then every 8 ( $\pm$  2) weeks thereafter, and at follow up. Radiographic assessment is not mandatory during these time intervals.
- m Following enrollment and initiation of IP, the first cycle of chemotherapy during the treatment period should not be administered until platelet counts are  $\geq 100 \times 10^9/L$  or until **at least week 4**, whichever comes first (see Section 7.4.1.2). **Do not start the first cycle of on-study chemotherapy before study week 2.** Thereafter, non-Amgen, non-investigational chemotherapeutic agents will be administered for the treatment of primary malignancy according to chemotherapy dose modification guidelines outlined in Section 7.4.1.2. Chemotherapy administration, including information about planned and actual chemotherapy dose and schedule, should be recorded throughout 3 on study cycles, at the follow up at one week after the last dose of IP, SFU 1 and SFU 2. The start of the planned chemotherapy must be no more than 2 days after the local laboratory assessments have been taken **during the study visit.**
- n For subjects who discontinue IP prior to completing 3 cycles of chemotherapy, platelet transfusions should be recorded through 3 on-study chemotherapy cycles.
- o [REDACTED]

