### 9.2.3.1 Adverse Events

#### 9.2.3.1.1 Time Period and Frequency for Collecting and Reporting Safety Event Information

##### 9.2.3.1.1.1 Adverse Events

The adverse event grading scale to be used for this study will be the CTCAE version 5.0 and is described in [Appendix 4](#).

Adverse events possibly related to any study procedures are reported after signing of the ICF. All other adverse events are reported after the first dose of protocol-required therapies (romiplostim/placebo [investigational product], chemotherapy [non-investigational product] up to 3 cycles). The investigator is responsible for ensuring that all adverse events observed by the investigator or reported by the subject that occur after signing of the ICF or from the first dose of protocol-required therapies, as specified above, through the 30 (+5) days after the last dose of protocol-required therapies (last dose of investigational product and last dose of last cycle [up to 3 cycles] of chemotherapy non-investigational product) are reported using the Event CRF. If mandated by country-specific requirements, non-serious adverse events will be collected through the whole duration of the LTFU period until EOS.

Note: For subjects who discontinue investigational product prior to completing 3 cycles of chemotherapy, non-serious adverse events should be collected through 3 on-study chemotherapy cycles.

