##### 9.2.3.1.1.2 Serious Adverse Events

The investigator is responsible for ensuring that all serious adverse events observed by the investigator or reported by the subject that occur after signing of the informed consent through the end of study are reported using the Event CRF.

All serious adverse events will be collected, recorded and reported to the sponsor or designee within 24 hours, as indicated in [Appendix 4](#). The investigator will submit any updated serious adverse event data to the sponsor within 24 hours of it being available.

The criteria for grade 4 in the CTCAE version 5.0 grading scale differs from the regulatory criteria for serious adverse events. It is left to the investigator's judgment to report these grade 4 abnormalities as serious adverse events. **For any adverse event that applies to this situation, comprehensive documentation of the event's severity must be recorded in the subject medical records.**

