Duration-Adjusted Event Rate for AE during the Follow-up Period

The duration-adjusted AE incidence rate within a treatment group is expressed as the number of events per 100 subject-years from the 31 days after the date of last dose of investigational product to EOS:

$$\text{Duration-adjusted event rate} = \frac{\text{Total number of events}}{\text{Total duration in subject-years}} \times 100$$

Endpoints: Primary - No Thrombocytopenia-induced Modification of any Myelosuppressive Treatment Agent in the Second and Third Cycles

Subjects will meet the criteria of the primary endpoint if there is no thrombocytopenia-induced modification of any myelosuppressive treatment agent in the second and third cycles of the planned on-study chemotherapy regimen.

A thrombocytopenia-induced modification is defined as any dose reduction, dose delay, dose omission, and/or early chemotherapy treatment discontinuation due to low platelet counts less than $100 \times 10^9/\text{L}$.

For the purposes of determining dose reductions, the actual on-study chemotherapy doses will be compared to the planned chemotherapy dose recorded on study day 1, defined by the dose administered in the chemotherapy cycle immediately prior to study entry.

For the purposes of determining dose delays, the difference between the start date of a given chemotherapy cycle and the start date of the chemotherapy cycle immediately prior to the given cycle will be calculated and compared to the planned cycle length of the regimen.

Delayed, reduced, omitted, and discontinued doses within a cycle will also be counted as dose modifications even if they do not cause the start of the next cycle to be delayed. Note: For subjects who discontinue investigational product prior to completing 3 cycles of chemotherapy, chemotherapy dose and schedule should be recorded through 3 on-study chemotherapy cycles to the end of the third on-study cycle.

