**9.6 Safety Analyses****9.6.1 Analyses of Primary Safety Endpoint(s)**

The Medical Dictionary for Regulatory Activities (MedDRA) version 25.1 or later will be used to code adverse events. The adverse events will be summarized by treatment group using the safety analysis set.

The subject incidence will be summarized for all **TEAEs**, serious **TEAEs**, **TEAEs** leading to withdrawal of investigational product, **TEAEs** leading to withdrawal of chemotherapy agent,

treatment-related TEAEs, serious treatment-related TEAEs, grade ≥ 3 TEAEs, and fatal TEAEs by system organ class and preferred term.

In addition, subject incidence and duration-adjusted rates for events of interest will be summarized. Subject listing of all adverse events occurred from the first dose of IP to 30(+5) days after last dose of the IP or last dose of on-study chemotherapy (up to 3 cycles), whichever occurs later, will be provided. A separate listing will be provided for all the AEs (including AEs starting in LTFU period).

An Independent Biostatistics Group (IBG) will perform periodic safety analyses for review by an independent DMC. DMC will review all available safety data on a regular basis during the study and will make recommendations concerning the continuation or alteration of the study based on its data review. More details are included in the DMC charter.

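### The SAP's follow-up-period adverse event rate counts person-time to end of study, but non-serious events are mostly not collected that long, so any rate that includes them is understated

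*SAP*

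**What the plan says.** SAP Section 5 (Definitions) has two duration-adjusted adverse event rates. The treatment-period rate stops at last IP plus 30 days or EOS, whichever is earlier. The follow-up-period rate is "expressed as the number of events per 100 subject-years from the 31 days after the date of last dose of investigational product to EOS". Its formula is total events over total subject-years, times 100; it does not separate serious from non-serious events.

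The protocol's collection rules differ by seriousness:

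- Routine collection (Section 2.2, Schedule of Activities, footnote k): "Both non-serious adverse events and serious adverse events will be collected through 30 (+5) days after the last dose of protocol-required therapies", meaning IP and up to three cycles of on-study chemotherapy.
- Early IP stop (same footnote): "For subjects who discontinue IP prior to completing 3 cycles of chemotherapy, non-serious adverse events should be collected through 3 on study chemotherapy cycles".
- Serious events (same footnote): "Serious adverse events will be collected through the EOS". Section 9.2.3.1.1.2 agrees: serious events "that occur after signing of the informed consent through the end of study are reported using the Event CRF".
- Long-term follow-up (footnote k): "non-serious adverse events will be collected through EOS only if mandated by country-specific requirements". Section 9.2.3.1.1.1 repeats this: "If mandated by country-specific requirements, non-serious adverse events will be collected through the whole duration of the LTFU period until EOS".

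On outputs, SAP Section 9.6.1 says that "subject incidence and duration-adjusted rates for events of interest will be summarized", without naming the period. It also plans a listing that runs to 30 (+5) days after the later of last IP and last on-study chemotherapy, and a separate listing of all events including those in long-term follow-up.

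**The concern.** A rate per subject-year is interpretable only if every unit of time in the denominator is time in which an event could have been recorded. For serious events the window from day 31 to EOS meets that condition. For non-serious events it does not: outside the countries that mandate longer collection, most of that time is unobserved, yet it is counted as event-free.

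Protocol Section 10.3.2.3.1 gives hemorrhage and thrombotic/thromboembolic events as examples of events of interest, and some of these can be non-serious. If the follow-up-period definition were used for them, the reported off-treatment rate would partly reflect when collection stopped. It would also average over countries where collection stopped and countries where it did not.

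**Working it through.** The documents give no expected adverse event rate or count, so there is no planned figure to reproduce. The check is how much of the denominator is observed for non-serious events.

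**Inputs**

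- Study duration per subject: about 14 to 50 months (Protocol 5.3.2).
- Screening: up to 28 days. IP: 7–21 weeks for most subjects (Protocol 5.1).
- Individual EOS: tied to the last subject's 1-year visit (Protocol 9.1.6).
- Non-serious collection after day 30 post-IP, *w*: 0–5 days if IP and chemotherapy end together, from the 30 (+5) day rule. If IP stops early, *w* is taken as 28–63 days; this is an assumption.
- Constant event rate and survival to EOS: assumptions.

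**Step 1. Denominator, T (day 31 after last IP to EOS)**

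- With one year of follow-up after last IP: 365 − 30 = 335 days.
- At 50 months: 50 × 30.44 = 1522 days. Less 28 (screening), 49 or 147 (treatment) and 30, this is 1415 or 1317 days.

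**Step 2. Fraction observed for non-serious events, w/T**

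| | T = 335 | T = 1317–1415 |
|---|---|---|
| IP and chemotherapy end together (w = 0–5) | 0–1.5% | 0–0.4% |
| IP stops early (w = 28–63, assumed) | 8–19% | 2–5% |

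The non-serious rate is understated by one minus these fractions, so by roughly 80% to 100%. For serious events the fraction is 1.00. In a country that mandates collection to EOS, the fraction is also 1.00 for non-serious events. The documents do not say how many subjects come from such countries.

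**Step 3. All events together**

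With *s* the serious share of events, the captured fraction is s + (1 − s) × w/T. The documents give no *s*. Over the values of *w* and T above:

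- s = 0.10: 0.10 to 0.27
- s = 0.25: 0.25 to 0.39
- s = 0.50: 0.50 to 0.59

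**Step 4. Would the arms differ?**

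Only if the frequency of early IP stopping differs by arm. For illustration, take w = 42 days for early stoppers and 2.5 for others, with equal true rates (all assumed). Mean observed days are f × 42 + (1 − f) × 2.5, where *f* is the share stopping early.

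- 30% in both arms: ratio 1.00.
- 30% placebo, 15% romiplostim: 14.35 and 8.43 days; non-serious rate ratio, romiplostim to placebo, 8.43/14.35 = 0.59.
- 50% placebo, 15% romiplostim: 22.25 and 8.43 days; ratio 8.43/22.25 = 0.38.

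For all events with 25–50% serious, the two unequal cases give ratios of about 0.90 to 1.00.

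**The case against.** The strongest defence is that no planned table is shown to use this rate. SAP 9.6.1 does not name the follow-up period for its events-of-interest rates. Protocol 10.3.2.3.1 places events of interest within the treatment-emergent summary, and the SAP ends treatment-emergent status 30 days after last IP. The only output that SAP 9.6.1 names for long-term follow-up events is a listing. This stands as a limit on the consequence. It does not remove the mismatch: the SAP defines the rate, and no other use for it is evident.

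Second, serious events are collected to EOS in all subjects, so bleeds and thromboses that are fatal, life-threatening, lead to hospitalization or are otherwise medically important are captured. This stands, and it is why a serious-only rate is sound over the existing window.

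Third, follow-up ends at death and can end early on withdrawal, so some denominators are shorter than 335 days. This stands; the percentages apply to subjects followed at least one year after last IP.

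A reader might go further and infer that romiplostim will look safer in follow-up, because placebo subjects stop IP earlier for non-response and so have more observed time. The documents do not support that as a finding:

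- They give no IP-stop rates by arm. SAP Section 8.4 says only that placebo subjects might drop out earlier, and leaving the study ends events and person-time together.
- The maximum-dose non-response stop cannot occur before about week 13: a start at 2 µg/kg with weekly steps of 1 reaches 10 at week 9, and four weeks at that dose follow. Chemotherapy may start from week 4, and undelayed 14-day cycles from then put cycle 3 at week 8. Late starts or delays would be needed for that stop to create much extra observed time.
- The rate is a within-group description with the same rule in both arms, and no between-arm test is planned.

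**Conclusion.** The definition does not match the data collected. As written, a follow-up-period rate that includes non-serious events is understated. For subjects followed at least one year after last IP, about 0–1.5% of the denominator is observed for those events when IP and chemotherapy end together, and roughly 2–19% when IP stops early. The second range rests on the assumed 28–63 extra days; the first needs only the protocol's own windows and IP and chemotherapy ending together. The mixing of countries follows from the text, but its size cannot be computed because the number of subjects affected is not given.

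A difference between arms is possible, not established. The consequence is limited to a descriptive safety rate. The treatment-emergent tables, the treatment-period rate and the grade 2 or higher bleeding endpoint stop at last IP plus 30 days or earlier, and the MDS and secondary-malignancy analyses are separate time-to-event analyses; none is affected. The definition should be corrected, but the trial's main conclusions do not depend on it.

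**What to change.** In SAP Section 5, restrict the follow-up-period rate, from day 31 after last IP to EOS, to serious adverse events. State in SAP 9.6.1 that any follow-up-period rate for events of interest uses this definition.

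If an all-event rate after day 30 is also shown, end both events and person-time at 30 days after the later of last IP and last on-study chemotherapy, or at EOS if earlier, in all countries. This follows the window that SAP 9.6.1 already uses for its listing, without the 5-day visit allowance. Subjects whose IP and chemotherapy end together then contribute almost no time, so this rate would rest mainly on early IP stoppers, a selected group. It should be labelled as such, shown with its person-time, and not used as the main off-treatment rate. Non-serious events from countries that collect to EOS stay in the long-term follow-up listing.

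The cost is SAP wording and, for the optional rate, one derived date; no new data are needed. The downside is that late non-serious events no longer enter the main follow-up rate.

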Endpoints: Secondary (3) – Duration-adjusted Event Rate of \geq Grade 2 Bleeding Events

The duration-adjusted event rate (**events/100 subject-years**) is defined as the number of grade ≥ 2 bleeding events, divided by the total duration (in 100 subject-years) that subjects have been on study from study day 1 to the earliest of last dose of IP + 30 days or EOS.

Bleeding events will be recorded on the adverse events case report form (CRF) and graded using the CTCAE version 5.0. Bleeding events will be identified using the narrow search of haemorrhages standardized MedDRA query (SMQ), using the MedDRA version 25.1 or later.

Abbreviations:

- b.events = Bleeding Events (Haemorrhages)
- Status = 1 (recurrence of b.event)
- Status = 0 (no b.event)

Censoring Rules:

- Subject with at least one or more than one “grade ≥ 2 b.events”
 - Subject may report multiple b.events, each b.event will be flagged with “Status = 1”.
 - Subject may report multiple b.events, if any b.event end date is missing then also “Status = 1”.
 - The treatment period from last b.event start date to Min(last dose of IP date+30, Study End date) will be considered as no event period, reported as “Status = 0”
- The subjects who do not report any “grade ≥ 2 b.events”
 - These subjects will be included in analysis with “Status = 0”.

Notes:

Status variable will be assigned considering “Haemorrhages” SMQ only, irrespective of number of other adverse event(s) experienced by subject.

- **Status is the censoring variable which will be utilized into the PHREG.**

Endpoints: Secondary (4) –Overall Survival

Overall survival time will be calculated from study day 1 to death. Subjects who have not died will be censored at their last date of contact.

Endpoints: Secondary (5) – Platelet Transfusion

Platelet transfusions during the treatment period is defined as a subject having at least one platelet transfusion after during study period as recorded on the transfusions CRF.

Endpoints: Secondary (6) – Achieving a platelet count $\geq 100 \times 10^9/L$

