Achieving a platelet count $\geq 100 \times 10^9/L$ at any time after study day 1, up to and including the date of the week 4 visit (ie, 7 days after the third planned dose of investigational product). if a platelet transfusion occurred during the 7 days preceding a platelet count, then that platelet count will not be considered as achieving the endpoint even if it is $\geq 100 \times 10^9/L$. Subjects who have no platelet counts during this period will be considered as not achieving achieved a platelet count $\geq 100 \times 10^9/L$. For subjects who never received IP, the subjects are considered as not achieving a platelet count $\geq 100 \times 10^9/L$. Weeks with no platelet count measurements (missing data) are considered as not achieving a platelet count $\geq 100 \times 10^9/L$.

Endpoints: Secondary (safety) – Myelodysplastic Syndromes (MDS) Free Time

Myelodysplastic syndromes (MDS) free time is defined as the time from the first dose of IP to the first occurrence of MDS. Subjects who have not had an MDS event will be censored at their last contact date or death date, whichever is later.

It is calculated as:

Date of first occurrence of MDS or censoring date – the date of the first dose of IP + 1.

MDS events will be identified using the narrow search of myelodysplastic syndromes (SMQ), using the MedDRA version **25.1** or later available at the time of the analysis.

Endpoints: Secondary (safety) – Myelodysplastic Syndromes (MDS) Free Survival Time

MDS free survival time is defined as the time from the first dose of IP to the first occurrence of MDS or death, whichever is earlier. Subjects who have not had an MDS event and have not died will be censored at their last contact date. It is calculated as:

Date of first occurrence of MDS, death or censoring – the date of the first dose date of IP + 1.

MDS events will be identified using the narrow search of myelodysplastic syndromes (SMQ), using the MedDRA version **25.1** or later available at the time of the analysis.

Endpoints: Secondary (safety) – Secondary Malignancy Free Time

[figure not shown]
Secondary malignancy free time is defined as the time from the first dose of IP to the onset of a secondary malignancy. Subjects without an event will be censored at their last contact date or death, whichever is later. It is calculated as:

Date of onset of secondary malignancy or censoring – the date of the first dose IP + 1.

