Endpoints: Secondary (safety) – Secondary Malignancy Free Survival Time

Secondary malignancy free survival time is defined as the time from the first dose of IP to the onset of a secondary malignancy or death, whichever is earlier. Subjects without an event will be censored at their last contact date. It is calculated as:

Date of onset of secondary malignancy, death or censoring – the date of the first dose date of IP + 1.

Last Contact Date

The latest date on which a subject is known to alive.

Myelosuppressive Treatment Agents

Myelosuppressive treatment agents are those agents in the on-study chemotherapy regimen that are 5-fluorouracil **or capecitabine and oxaliplatin (plus irinotecan in FOLFIRINOX or FOLFOXIRI) (Oxaliplatin)-based chemotherapy regimen.**

On-study Chemotherapy Regimens

The on-study chemotherapy regimen is the chemotherapy regimen planned to be taken after study day 1. It will be the same chemotherapy regimen taken in the last chemotherapy cycle immediately before study day 1.

Platelet Counts

If there are multiple platelet values performed on a study visit date, the platelet value most immediately prior to **non-IP** administration **will be selected**, as the platelet value for that study visit date. **If no platelet value prior to non-IP administration, the platelet value prior to IP administration will be selected.**

Prior Use of Medication at Baseline

Prior use of medication at baseline means the medication has been administered prior to the start of the current chemotherapy regimen.

Randomization Date

Randomization date is defined as the date the subject is randomized to a treatment group. Per protocol, subjects should initiate IP the same day they are randomized.

Study Day 1

Study day 1 is defined as the randomization date. **If the randomization date and the first IP administration date are the same, then study day 1 is the randomization date for both efficacy and safety analysis.**

If randomization date and subject first IP administration date are different then study day 1 will be derived using first IP administration date.

Study Day

For dates occurring on or after the study day 1 date, study day will be calculated as:

Date of interest - **date of first IP administration** + 1.

For dates occurring before the study day 1 date, study day will be calculated as:

Date of interest - **date of first IP administration.**

Treatment-emergent Adverse Event

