6.1 Full Analysis Set

The full analysis set will include all randomized subjects. All subjects will be analyzed according to the treatment to which they are randomized. Full analysis set will be used for all primary analysis for primary and secondary efficacy endpoints.

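### The SAP's study day 1 override is not limited to safety analyses, so late-dosed subjects start overall survival and time to platelet response after randomization, and never-dosed subjects are handled inconsistently

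*SAP*

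**What the plan says.** All the relevant definitions are in SAP Section 5.

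- **Default.** "Study day 1 is defined as the randomization date". When the randomization and first IP dates coincide, the SAP says this holds for efficacy and safety alike.
- **Override.** "If randomization date and subject first IP administration date are different then study day 1 will be derived using first IP administration date". No analysis type is named.
- **Study Day formula.** "Date of interest - date of first IP administration + 1" for dates on or after study day 1. It uses the first IP date only.
- **Expected practice.** "Per protocol, subjects should initiate IP the same day they are randomized".
- **Overall survival.** "Overall survival time will be calculated from study day 1 to death".
- **Time to first platelet response.** Response date minus study day 1, plus 1. A subject with no post-baseline count is censored at the randomization date. Protocol Section 10.3.2.2.2.2 censors at study day 1 instead.
- **Bleeding.** The denominator is the time "that subjects have been on study from study day 1 to the earliest of last dose of IP + 30 days or EOS".
- **Week-4 response.** "For subjects who never received IP, the subjects are considered as not achieving a platelet count" of the required level, so the SAP foresees never-dosed subjects.

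SAP Section 6.1 sets the population for primary and secondary efficacy: "The full analysis set will include all randomized subjects".

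The protocol also ties day 1 to the first dose and expects it on the randomization date (Schedule of Activities footnote e, Section 9.1.2, Appendix 1). It gives no rule for when the dates differ.

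**The concern.** An all-randomized analysis of a time-to-event endpoint normally starts every subject's clock at randomization. Under the override, subjects dosed on time start there and subjects dosed late start at the dose. That gives mixed origins in two endpoints of the fixed testing sequence. It also sets the override against the SAP's own censoring rule, which still refers to randomization.

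Never-dosed subjects raise a separate difficulty. They have a time zero under the default sentence but no study day under the formula, so two programmers could build different datasets. In the bleeding endpoint the last-dose limit does not exist for them, so the window stays open to EOS. That is well beyond the period in which non-serious bleeds are collected.

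**Working it through.** The plan states no figure for this point, so the check compares definitions and does date arithmetic with assumed dates.

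**1. Late-dosed subject, overall survival.** Assume death 200 days after randomization. Time = death date - time zero + 1.

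| First dose after randomization | From randomization | Under the override |
|---|---|---|
| 0 days | 201 | 201 |
| 1 day | 201 | 200 |
| 7 days | 201 | 194 |

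The loss equals the dosing delay. A response dated after the first dose shifts by the same number of days.

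**2. Late-dosed subject, time to response, no post-baseline count.** The censoring date is randomization.
- 7-day delay: 0 - 7 + 1 = -6 days.
- 1-day delay: 0 - 1 + 1 = 0 days.
- Time zero at randomization: 0 - 0 + 1 = 1 day.

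Whether this arises depends on what counts as post-baseline. Under SAP Section 5, baseline is the randomization-date value, so a count taken at a later first dose is post-baseline and censoring falls on or after time zero. Under SAP Section 3.1, the baseline platelet count is the last one before planned IP. On that definition the count at first dose may itself be baseline, and censoring drops back to randomization.

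**3. Never-dosed subject.** Assume death 20 days after randomization. The override compares two dates and this subject has one, so the default applies: 20 - 0 + 1 = 21 days. The Study Day formula has no first IP date and returns missing.

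**4. Never-dosed subject, descriptive bleeding rate.** Inputs:
- 54 placebo and 108 romiplostim subjects (SAP Section 3.2).
- IP for 7 to 21 weeks (SAP Section 3.1); 12 weeks is my assumed central value.
- Window of IP time plus 30 days.
- Study duration of 14 to 50 months (Protocol Section 5.3.2).
- Event count unchanged.

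Placebo subject-years = 54 x (weeks/52.18 + 30/365.25).

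| Weeks of IP | Placebo subject-years | Rate falls, +14/12 years | Rate falls, +50/12 years |
|---|---|---|---|
| 7 | 11.7 | 9.1% | 26.3% |
| 12 | 16.9 | 6.5% | 19.8% |
| 21 | 26.2 | 4.3% | 13.7% |

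Each fall is added time / (base + added time). At 12 weeks these are 1.17/(16.85 + 1.17) and 4.17/(16.85 + 4.17). Counting the never-dosed subject among the 54 (53 dosed, 16.54 subject-years) gives 6.6% and 20.1%. In the romiplostim arm, 108 subjects contribute 33.7 subject-years and the fall is 3% to 11%.

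These are upper-end illustrations. The 14 to 50 months include up to 4 weeks of screening, and the subject is assumed to stay to EOS. Bleeding is evaluated at the primary analysis (SAP Section 7.2), when a data cut-off would shorten the tail.

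**5. Bleeding test.** The Andersen-Gill partial likelihood uses only the risk sets at event times. Once the other subjects in a stratum are censored at last IP + 30 days, one remaining subject's event-free tail adds nothing to the hazard ratio or p-value.

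**6. Frequency.** The documents give none. If 1% to 5% of 162 were never dosed (assumption), that is about 2 to 8 subjects, each 0.6% of the full analysis set.

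**The case against.** The strongest reply is that dosing is planned for the randomization day, so the override should seldom operate. The trial is double-blind, so any delay is unlikely to differ by arm. The protocol itself anchors day 1 on the first dose. All of this stands, and it makes the point one of consistent definition rather than demonstrated bias.

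Several stronger readings are tempting, and the documents do not support them.

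- **Never-dosed subjects have no time zero and drop out of the survival and response analyses.** A reader might infer this from the Study Day formula. But the override needs two differing dates, so the default stands, and neither endpoint is defined through that formula.
- **Deaths before dosing are lost.** A subject who dies before dosing was never dosed, keeps the randomization date, and the death counts.
- **Only the week-4 endpoint covers never-dosed subjects.** Time to response has the randomization-date censoring rule. Platelet nadir uses the baseline count if on-study chemotherapy never starts. Missing cycle 2 or 3 visits without a platelet count are primary-endpoint failures (SAP Section 8.3).
- **The SAP alone moved the origin.** The protocol already ties day 1 to the first dose. What the SAP adds is the explicit rule for differing dates.
- **The 6% to 20% fall distorts the confirmatory bleeding test.** It applies to the descriptive rate only.

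A further objection is that starting every bleeding window at randomization would repeat the fault. Protocol Section 9.2.3.1.1.1 generally collects non-serious adverse events only from the first dose of protocol-required therapy, whether IP or chemotherapy. That is correct, and it shapes the fix.

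**Conclusion.** The point holds in limited form. The override reaches efficacy and gives late-dosed subjects a later origin than the all-randomized set implies. Overall survival and time to response shorten by exactly the delay. The SAP's censoring date for time to response can precede time zero, but only if a subject is dosed late and also has no count treated as post-baseline. For never-dosed subjects, the survival and response origins are defined but conflict with the Study Day formula, and the bleeding window has no sensible end.

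The size is nil if every subject is dosed on the randomization day. Otherwise it is a few days per late-dosed subject. For one never-dosed placebo subject followed to EOS, the descriptive placebo bleeding rate falls about 6% to 20% at 12 weeks of IP, or 4% to 26% across 7 to 21 weeks. The effect on the Andersen-Gill test is little or none. The primary endpoint does not use this clock. The delays, dates and never-dosed counts are assumptions.

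**What to change.** In SAP Section 5:

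1. State that for overall survival and time to first platelet response on the full analysis set, time zero is the randomization date for every subject, dosed or not.
2. Limit the first-IP-date override and the Study Day formula to safety analyses.
3. For bleeding, keep at-risk time within the period in which non-serious adverse events are collected. For dosed subjects the window can start at the first dose. Never-dosed subjects should not run to EOS; for example, they would contribute to the descriptive rate only time inside that collection period, and none if they received no protocol-required therapy.

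Because the protocol equates day 1 with the first dose, record items 1 and 3 in SAP Section 10, which now reports no changes from the protocol. The cost is a few sentences and minor dataset programming, with no new data. It is best settled before unblinding.
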